2. LIST OF ABBREVIATIONS

Abbreviation	Definition	
4CMenB	bexsero vaccine	
CIOMS	International Ethical Guidelines for Epidemiological Research issued by the Council for International Organizations of Medical Sciences	
CFR	Code of Federal Regulations	
СРТ	current procedural terminology	
EMA	European Medicines Agency	
ENCePP	European Network of Centres for Pharmacoepidemiology and Pharmacovigilance	
FDA fHBP	Food and Drug Administration factor H binding protein	
GEP	Good Epidemiological Practice	
GPP	Good Pharmacoepidemiology Practices	
HRs	hazard ratios	
HIPAA	Health Insurance Portability and Accountability Act	
HIV	human immunodeficieny virus	
ICD-10-CM	International Classification of Diseases, 10 th Revision, Clinical Modification	
IEA	International Epidemiological Association	
IEC	Independent Ethics Committee	
IRB	Institutional Review Board	
ISPE	International Society for Pharmacoepidemiology	
ISPOR	Good Outcomes Research Practices issued by the International Society for Pharmacoeconomics and Outcomes Research	
MenB	Meningococcal Serogroup B	
MSM	men who have sex with men	
NDC	National Drug Codes	
OMV	outer membrane vesicle	
PASS	Post-Authorization Safety Study	

PFIZER CONFIDENTIAL

CT24-WI-GL02-RF02 4.0 Non-Interventional Study Protocol Template For Secondary Data Collection Study 01-Jun-2022 Page 4 of 22

Abbreviation	Definition
SAS	statistical analysis system
US	United States
VE	Vaccine effectiveness

4. ABSTRACT

Not required.

5. AMENDMENTS AND UPDATES

None.

6. MILESTONES

Milestone	Planned date
Start of data collection	20 April 2023
End of data collection	30 April 2023
Final study report	31 October 2023

7. RATIONALE AND BACKGROUND

This study is not a Post-Authorization Safety Study (PASS) and is not a commitment to any regulatory authority.

Meningococcal B outer membrane vesicle (OMV) vaccines have been created, developed and used to control outbreaks of meningococcal B diseases in New Zealand, Norway and Cuba. Studies suggested that OMV vaccines could potentially protect against gonococcal infections in New Zealand and Norway.¹

Recently 4 studies described the effect of Bexsero (4CMenB) on gonococcal infection in adolescents and young adults (2 studies in the United States (US), 1 in Australia and 1 in Italy). The vaccine coverage differed by studies (69% in Australia, 33% in men who have sex with men (MSM) living with human immunodeficiency virus (HIV) in Italy and 1.8% in New York City & Philadelphia. The direct effect of 4CMenB (vaccine effectiveness) ranged from 32 to 74% for 2 full doses and 33 to 71% for at least 1 dose.²⁻⁵

Abara et al studied the effectiveness of 4CMenB and factor H binding protein (fHbp) vaccines in 2 separate studies using the same methodology in New York and Philadelphia regions for the period of 2016-2018 (the first 2 years of meningococcal serogroup B [MenB] vaccines use in the US). The vaccine coverage was 7.4% and 1.6% for at least one dose for 4CMenB and fHbp vaccines respectively. The effectiveness of 4CMenB was 40% (95% CI 23; 53) for full dose and 26% (95% CI 12; 37) for only 1 dose. The effectiveness of fHbp vaccine was 3% (95%CI: \pm 19; 21).⁶ 6These results were based on data during the period where fHbp had extremely low vaccine coverage (<2%).

The vaccine effectiveness for 4CMenB varied highly according to study types, age of the study population and the vaccine coverage rate. The vaccine coverage had increased to 32% for any MenB vaccines in 2021 while it was 14% and 17% in 2017 and 2018 respectively. The effectiveness of fHbp vaccine observed in Abara et al study could be confirmed in a larger population with higher vaccine coverage. The purpose of the study will be to evaluate the effect of fHbp vaccine in prevention of gonococcal infection among 15-30 years in the US using the claim database.

8. RESEARCH QUESTION AND OBJECTIVES

8.1. Objectives

8.1.1. Primary Objective

To examine the effect of at least 1 dose of Trumenba on gonococcal infection in adolescents and young adults of 15-30 years in the US.

8.1.2. Secondary Objectives

- 1. To examine the effect of at least 2 doses of Trumenba on gonococcal infection in adolescents and young adults of 15-30 years in the US.
- 2. To examine the effect of at least 1 dose of Trumenba on chlamydial infection in adolescents and young adults of 15-30 years in the US.
- 3. To examine the effect of at least 2 doses of Trumenba on chlamydial infection in adolescents and young adults of 15-30 years in the US.

8.1.3. Exploratory Objectives

- 1. To examine the effect of at least 1 dose of Trumenba on gonococcal infection in adolescents and young adults of 16-23 years in the US.
- 2. To examine the effect of 1 dose of Trumenba on gonococcal infection in adolescents and young adults of 15-30 years in the US at 12 months, 24 months, 36 months and 48 months following the index vaccination.

9. RESEARCH METHODS

9.1. Study Design

This is a retrospective cohort study using health care administrative claims data as described in Section 9.4 Data Sources.

Adolescents and young adults approximately 15 to 30 years of age at their individual time zero (calculated based on birth year) will be identified from administrative claims during 01 January 2016 and 31 December 2021.

The exposure cohort will be the individuals who have received at least 1 dose of Trumenba and at least 1 dose of MenACWY (Menactra[®], Menveo[®], or MenQuadfi[®]) prior to the Trumenba vaccination, between 01 January 2016 and 31 December 2021. The index date (zero time) for the exposed cohort is the last date of vaccination, and the cohort will be followed from 14 days after vaccination to the end of the study period (31 December 2022). The individuals in the cohort will be censored by the event of interest, death date (if known), plan disenrollment (if known) or the end of the study period, whichever comes first.

PFIZER CONFIDENTIAL CT24-WI-GL02-RF02 4.0 Non-Interventional Study Protocol Template For Secondary Data Collection Study 01-Jun-2022 Page 11 of 22

The reference cohort will be those with at least 1 dose of MenACWY vaccine, but no doses of Trumemba during the observation period, received between 01January 2016 and 31 December 2021. The MenACWY-only vaccinated cohort is used as a reference cohort rather than an unvaccinated cohort in order to help control for theoretical differences in health seeking and risk behaviors between vaccinated and unvaccinated individuals. The index date (zero time) of the reference cohort is the last dose of MenACWY and these individuals will be followed from 14 days after zero time until the earliest occurrence of the following: outcome of interest, death date (if known), plan disenrollment (if known) or 31 December 2022 (end of study period).

The outcomes of interest are gonococcal and chlamydial infections and only the first episode within the study period will be considered as event in case of repeated infections.

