2.1 STUDY DESIGN

This is a retrospective cohort study including individuals 15 to 30 years of age enrolled in a health plan covered by IQVIA PharMetrics® Plus during 1 Jan 2016 to until the latest release of the data (October 2022). The study is to estimate the effect of Trumenba vaccination on the disease of interest, in particular, the gonococcal incidences will be compared between the recipients of Trumenba + MenACWY vaccines and the recipients of MenACWY vaccine.

The exposure cohort will be the individuals who have received at least one dose of Trumenba and at least one dose of MenACWY between 1 January 2016 and 31 December 2021. The non–exposure or reference cohort will be the individuals with no dose of Trumenba but at least one dose of MenACWY vaccine received during the same time period.

PFIZER CONFIDENTIAL CT24-WI-GL03-RF03 2.0 Non-Interventional Statistical Analysis Plan For Secondary Data Collection Study 01-Jun-2020 Page 4 of 28 The date of index vaccination (zero time) for the exposed cohort is the date of the last dose of Trumenba vaccination, after at least one dose of MenACWY. Trumemba and MenAWCY will be identified by Current Procedural Terminology® (CPT) codes and National Drug Codes (NDC) listed in Appendix Tables 4 and 3, respectively. The index date of the unexposed cohort is the first date of MenACWY vaccination. The diseases of interest are gonococcal infection and chlamydia infections occurring at least 14 days after the zero time. International Classification of Diseases, Tenth Revision, Clinical Modification (ICD-10-CM) codes listed in Appendix Table 1 and 2 will identify gonococcal and chlamydia infections, respectively. Only the first episode will be considered as the event in case of repeated infections. Individuals will be followed until the earliest occurrence of the following: outcome, at death date (if known), at plan disenrollment or end of study period.

Study population

This is a retrospective cohort study and the study population are adolescents and young adults approximately 15 to 30 years of age at their date of vaccination (calculated based on birth year) and will be identified from administrative claims during 01 January 2016 and 31 December 2021.

Data source

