7.2.1.1 Primary Endpoint - Main Analysis

Vaccination Status

If a participant received at least one dose of Trumenba and at least one dose of MenACWY vaccine will be considered as vaccinated (exposed population).

Analysis

We will assess gonococcal infection that occurred between 14 days after zero time and till end of the study period. We will censor the data at death date (if known), plan disenrollment, or the end of the study period, whichever comes first. In descriptive analyses, we will fit Kaplan-Meier curves. We will also create unadjusted and covariate adjusted Cox proportional hazard regression models with time varying approach verifying first that the proportionality assumption was satisfied for all independent variables. Since the individuals entered into the surveillance at different points of time, we will employ the computing process algorithm of the proportional hazard model where the date of entry and the date of end of follow-up will be used in the model instead of time contribution to compute the hazard ratios.

Hazard ratios (HRs) will be estimated by exponentiation of the coefficient for the vaccine variable in these models, with vaccine effectiveness estimated as $(1-HR)\times100\%$. Standard errors (SEs) for the coefficients will be used to estimate p-values and 95% CIs for the HRs. If a covariate does not satisfy the assumption of proportionality, we will exclude the variable for the multivariable model and will perform the stratified analysis using the covariate. Both crude and adjusted VE with its corresponding 95% CI will be calculated.

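### Reference-cohort membership depends on never receiving Trumenba later, so later recipients' unexposed time and infections count in neither cohort

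*Protocol*

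**What the plan says.** **Reference cohort.** Protocol 9.1 requires at least one MenACWY dose "but no doses of Trumemba during the observation period". SAP 2.1 describes people "with no dose of Trumenba but at least one dose of MenACWY vaccine received during the same time period". Follow-up starts 14 days after zero time. In the protocol, "The index date (zero time) of the reference cohort is the last dose of MenACWY"; in the SAP, "The index date of the unexposed cohort is the first date of MenACWY vaccination".

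**Exposed cohort.** Protocol 9.1 requires MenACWY before Trumenba, and "The index date (zero time) for the exposed cohort is the last date of vaccination". SAP 2.1 gives "the date of the last dose of Trumenba vaccination, after at least one dose of MenACWY". Follow-up again starts 14 days later.

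**End of follow-up.** Both documents list the outcome, death, disenrollment and end of study. Neither lists a switch or censoring at a Trumenba dose.

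**Model.** SAP 7.2.1.1 plans unadjusted and "covariate adjusted Cox proportional hazard regression models with time varying approach" and a counting-process layout. The reason it gives is that people enter at different times. The layout uses one entry date and one end date per person, and the same section assigns vaccination status once per person.

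**The concern.** Whether a person belongs to the reference cohort at zero time is decided by what happens afterwards. Someone given MenACWY in one year and Trumenba two years later was unexposed for those two years, but is not counted as unexposed.

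The omission does no harm if later uptake is unrelated to infection. If a gonorrhoea diagnosis, or the care around it, changes the chance of later vaccination, reference events are removed or retained selectively. The reference rate is then wrong, and so is VE. The target VE is only 20% (Protocol 9.5, SAP 3), so a shift of a few points matters. The limitations in Protocol 9.9 cover residual confounding and unrecorded Trumenba doses, not this mechanism.

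**Working it through.** **1. Where the gap goes.** Follow a person with MenACWY first and Trumenba later.

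- MenACWY to Trumenba, reference cohort: not counted, because a Trumenba dose follows.
- MenACWY to Trumenba, exposed cohort: not counted, because zero time is the last Trumenba dose.
- SAP 7.2.1.1: one entry date, one end date and one fixed status per person give no row in which the person is unexposed and then exposed.

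**2. The plan's power figure, and the time at stake.** Inputs from SAP 3: 500,000 people, 15% exposed (75,000 against 425,000), event probabilities 0.0036 and 0.0048, hazard ratio (HR) 0.80, two-sided alpha 0.05.

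- Events: 75,000 × 0.0036 + 425,000 × 0.0048 = 270 + 2,040 = 2,310.
- k = 75,000/425,000 = 0.1765.
- Power = Φ(√(k × 2,310) × 0.20/(0.80k + 1) − 1.96) = 94.3%, which reproduces the stated 94%.

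Let f be the mean MenACWY-to-Trumenba gap as a share of mean reference follow-up. The documents do not give f, so I assume 0.1 to 1.0. Restored reference time is 75,000f/425,000, or 1.8% to 17.6%. The events expected in it are 75,000f × 0.0048, or 36 to 360. Power becomes 94.3% to 94.7%.

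**3. Size of the bias.** Inputs:

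- True VE 20% (Protocol 9.5, SAP 3).
- Later uptake u = 15%, borrowed from the SAP's exposed share, and 5% as an assumed lower value.
- m, the factor by which a diagnosis multiplies the later uptake rate: assumed 2, 1.5 and 0.5.
- Uptake at a constant rate over the first share w of follow-up: assumed w = 1 or 0.2.
- Rare events at a constant hazard.

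An undiagnosed person stays in the reference cohort with probability 1 − u. A person diagnosed with fraction s of the uptake window still to run stays with probability (1−u)^(1−s) × (1−u)^(ms). The ratio is (1−u)^((m−1)s). Averaging over s from 0 to 1:

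A = [(1−u)^(m−1) − 1] / [(m−1) ln(1−u)]

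Diagnoses after the window have ratio 1. The reference rate is therefore multiplied by F = (1−w) + wA, and VE reads 1 − 0.80/F. Example with u = 0.15, m = 2, w = 1: F = (0.85 − 1)/ln 0.85 = 0.9230, and VE = 1 − 0.80/0.9230 = 13.3%.

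As an upper bound, let every diagnosis precede all uptake: F = (1−u)^(m−1).

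| Setting | m = 2: F, VE | m = 1.5: F, VE | m = 0.5: F, VE |
|---|---|---|---|
| u = 15%, all follow-up | 0.9230, 13.3% | 0.9604, 16.7% | 1.0418, 23.2% |
| u = 15%, first fifth | 0.9846, 18.7% | 0.9921, 19.4% | 1.0084, 20.7% |
| u = 5%, all follow-up | 0.9748, 17.9% | 0.9873, 19.0% | 1.0129, 21.0% |
| u = 15%, upper bound | 0.8500, 5.9% | 0.9220, 13.2% | 1.0847, 26.2% |

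With m = 1, F = 1 and VE reads 20% in every row.

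**The case against.** **The SAP may already intend time-varying exposure.** The words in 7.2.1.1 allow that hope, and the counting-process layout could carry it. But the stated purpose is staggered entry, and a time-varying exposure would contradict the fixed cohort definitions in both documents. Correction is needed either way.

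**Adjustment and the chlamydia outcome give some protection.** This stands in part. Independence is needed only given age, sex and region. Chlamydia may reveal residual confounding, but Protocol 9.9 treats only HRs below 1.0 as a signal, and the comparison does not restore the missing time.

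**The bias may be small or absent, and the study is exploratory.** This stands. Early uptake leaves VE within about 1.3 points of 20% in the table. The 15% is a ceiling: the SAP excludes only Trumenba given before the first MenACWY dose, so same-day recipients could be exposed with no gap. The multipliers are assumptions.

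Three stronger readings are tempting and not supported:

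- That VE could plausibly read 6% or 26%. Those values require every diagnosis to precede all uptake.
- That VE is inflated. The direction depends on how a diagnosis changes later recorded uptake, and the documents do not say. Nor do they define the observation period.
- That the SAP leaves people first given Trumenba in 2022 unexposed through 31 December 2022. That end date is the protocol's. SAP 2.1 refers to an October 2022 data release, and its time-period phrase may qualify only the MenACWY dose. All that follows is that the end of study must be reconciled.

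**Conclusion.** The structural point holds. Reference membership depends on future vaccination, and the time and events between MenACWY and Trumenba are lost from both cohorts. Nothing in the SAP's model description repairs this.

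The effect on VE is about zero if later uptake is independent of infection given age, sex and region. Otherwise its direction is unknown. At 15% uptake and a true VE of 20%, diagnosis-related changes in uptake between halving and doubling give 13.3% to 23.2% when uptake is spread over follow-up, and 18.7% to 20.7% when it is early. At 5% uptake spread over follow-up the range is 17.9% to 21.0%. These figures rest on assumed uptake, timing and multipliers; they illustrate the size and do not predict it. The case for change is that the analysis relies on an untested assumption that the same data can remove.

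**What to change.** Remove the absence of later Trumenba as an entry condition. Make exposure explicitly time-varying in SAP 7.2.1.1 and in the cohort definitions of Protocol 9.1 and SAP 2.1:

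- **Unexposed time** runs from 14 days after MenACWY, or from reaching age 15 if later, until the first Trumenba dose.
- **Days 0 to 13** after the qualifying Trumenba dose count in neither group. Exposed time starts at day 14.
- **At-least-one-dose endpoints:** the qualifying dose is the first, so the last-dose zero time must be changed to match.
- **At-least-two-dose endpoints:** unexposed time still ends at the first Trumenba dose, so one-dose time does not enter the MenACWY-only comparator. Time from dose 1 to 14 days after dose 2 is excluded or modelled as a separate one-dose state. Exposed time starts 14 days after dose 2.
- **Age:** state that someone given MenACWY before 15 and Trumenba at 15 to 30 still contributes exposed time.
- **Infections in the gap:** under the first-episode rule, these become unexposed events that end follow-up. Say so.
- **Dates:** reconcile the MenACWY start (last dose in the protocol, first in the SAP; a last-dose start also depends on the future) and the end of study.

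The cost is start/stop recoding of the same claims and wording changes in both documents. No new data are needed, and power stays at about 94%.

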9.2. Setting

IQVIA PharMetrics[®] Plus is a longitudinal health plan database of adjudicated medical and pharmacy claims, including patient enrollment data for national and sub-national health plans and self-insured employer groups in the US. Administrative claims and enrollment data available during 01 January 2016 and 31 December 2022 will be used in this study.

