9.7. Data Analysis

The zero time is the date of Trumenba vaccination for the exposed group and the date of MenACWY for the unexposed group. We will assess gonococcal infections that occurred between i) 14 days after zero time and 365 days ii) 14 days after zero time and 730 days, iii) 14 days after zero time and 1095 days, and iv) 14 days after zero time and till end of the study period (31Dec2022). We will censor the data in the event of interest, death date (if known), plan disenrollment (if known), target end date, or the end of the study period, whichever comes first. In descriptive analyses, we will fit Kaplan-Meier curves. We will also create unadjusted and covariate adjusted Cox proportional hazard regression models verifying first that the proportionality assumption was satisfied for all independent variables. Hazard ratios (HRs) will be estimated by exponentiation of the coefficient for the vaccine variable in these models, with vaccine effectiveness estimated as (1–HR)×100%. SEs for the coefficients will be used to estimate p values and CIs for the HRs. If a covariate does not satisfy the assumption of proportionality, we will exclude the variable for the multivariable model and will perform the stratified analysis using the covariate.

Detailed methodology for summary and statistical analyses of data collected in this study will be documented in a statistical analysis plan (SAP), which will be dated, filed and maintained by Pfizer. The SAP may modify the plans outlined in the protocol; any major modifications of primary endpoint definitions or their analyses would be reflected in a protocol amendment.

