5 ENDPOINTS AND COVARIATES

5.1 EFFICACY/EFFECTIVENESS ENDPOINT(S)

5.1.1 Primary Endpoint

• VE calculated as 1 minus the hazard ratio for gonococcal infection between the recipients of both Trumenba (at least one dose) and MenACWY (at least one

PFIZER CONFIDENTIAL

CT24-WI-GL03-RF03 2.0 Non-Interventional Statistical Analysis Plan For Secondary Data Collection Study 01-Jun-2020 Page 8 of 28 dose) vaccines and the reciepients of MenACWY vaccine only multiplied by 100, adjusted for age, sex, and US region.

In this analysis, the cases are those who have at least one diagnosis code for gonococcal infection (Appendix Table 1) during follow-up. Each individual will be followed for the outcome from 14 days after their zero time until the end of the follow-up period, censoring the follow-up at death date (if known) or plan disenrollment (if known).

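### Infection before follow-up is handled inconsistently: the protocol's first-episode rule is not tied to zero time, and the SAP has no washout to separate a new episode from a repeat claim

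*Protocol*

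**What the plan says.** **Event rule, protocol.** Section 9.1 states that "only the first episode within the study period will be considered as event in case of repeated infections". It gives the end of the study period (31 December 2022) but no start. Section 9.2 adds: "Administrative claims and enrollment data available during 01 January 2016 and 31 December 2022 will be used in this study". Section 9.7 is tied to zero time: "We will assess gonococcal infections that occurred between i) 14 days after zero time and 365 days", and its longer windows also open at day 14. That sentence names gonococcal infection only.

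**Event rule, SAP.** Section 2.1 says "The diseases of interest are gonococcal infection and chlamydia infections occurring at least 14 days after the zero time" and then takes the first episode. Section 5.1.1 says "the cases are those who have at least one diagnosis code for gonococcal infection", with the code falling in follow-up. Secondary endpoints 2 and 3 (5.3.1) and both exploratory endpoints (5.3.2) ask instead for a claim in the database. Exploratory endpoint 1 also omits the 14-day start, which 7.2.3.4.1 restores.

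**Earlier infection.** No eligibility criterion (Protocol 9.2.1 and 9.2.2; SAP 4.1) addresses it, and no washout is set. The SAP 5.4 covariates are age, sex and US region.

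**Zero time.** Protocol 9.1: "The index date (zero time) for the exposed cohort is the last date of vaccination" and "The index date (zero time) of the reference cohort is the last dose of MenACWY". SAP 2.1 uses, for the exposed, "the date of the last dose of Trumenba vaccination, after at least one dose of MenACWY", but indexes the reference cohort at its first MenACWY dose.

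**Use of chlamydia.** Protocol 9.9 treats a hazard ratio below 1.0 for the reference disease as a sign of residual confounding that may lead to adjustment of the VE estimates. It gives no margin.

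**The concern.** Two programmers could build different event flags from these texts.

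On the literal reading of Protocol 9.1, someone infected in 2016 and vaccinated in 2018 has used up the first episode. That person stays in the denominator but cannot become a case. If such people are a larger share of one cohort, the hazard ratio shifts without any vaccine effect.

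On the SAP primary rule the opposite happens. With one code sufficient and no washout, a follow-up claim for an infection first coded before day 14 counts as incident, although the vaccine could not have prevented it.

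Either error can differ between cohorts if observed time before zero time differs. That depends on the index dates, and the two documents disagree about the reference cohort's. The reference outcome is the most exposed to this, because it is judged against exactly 1.0.

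**Working it through.** **1. The plan's own figures.** SAP section 3 assumes 500,000 people, about 15% exposed (75,000 against 425,000), event probabilities 0.0036 and 0.0048, HR 0.80 and two-sided alpha 0.05.
- Events: 75,000 × 0.0036 + 425,000 × 0.0048 = 270 + 2,040 = 2,310.
- With k = 75,000/425,000, power = Φ(√(k × 2,310) × 0.20/(0.80k + 1) − 1.96) = 94.3%, against 94% stated.
- Protocol 9.5: (1.960 + 0.842)²/(0.0046 × 1.50² × 0.22²) = 15,668.3, rounded up to 15,669 as stated.

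Both reproduce, and neither depends on the first-episode rule.

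**2. The literal reading.** Let q be the share of a cohort infected before zero time and r the hazard multiple for repeat infection. The documents give neither, so both are assumptions. The highest q used, 0.48%, equals the SAP's reference event probability. The share of a cohort's events that would be cancelled is L = qr/(1 − q + qr), and HR observed = HR true × (1 − L exposed)/(1 − L reference).

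Example: q exposed 0.24%, q reference 0.12%, r = 10. L exposed = 0.024/1.0216 = 0.0235 and L reference = 0.012/1.0108 = 0.0119. At a true HR of 1.00 the observed HR is 0.9765/0.9881 = 0.988, a spurious VE of 1.2 points.

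| q exposed / reference | r | HR observed if true HR is 1.00 | Shift in VE (points) | VE observed if true VE is 20% |
|---|---|---|---|---|
| 0.10% / 0.05% | 1 | 0.9995 | +0.05 | 20.04% |
| 0.10% / 0.05% | 20 | 0.9902 | +0.98 | 20.79% |
| 0.24% / 0.12% | 1 | 0.9988 | +0.12 | 20.10% |
| 0.24% / 0.12% | 5 | 0.9940 | +0.60 | 20.48% |
| 0.24% / 0.12% | 10 | 0.9882 | +1.18 | 20.94% |
| 0.48% / 0.24% | 20 | 0.9559 | +4.41 | 23.53% |
| 0.20% / 0.20% | 1 to 40 | 1.0000 | 0 | 20.00% |
| 0.10% / 0.20% | 20 | 1.0197 | −1.97 | 18.43% |

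More extreme inputs go further: 8.8 points at a true HR of 1.00 with q 0.48% against zero and r = 20, and 8.1 points with 0.48% against 0.24% and r = 40.

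In the +4.41 row about 24 exposed and 94 reference events are cancelled and power at HR 0.80 is 93.2%. The issue is bias and definition, not power.

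**3. The reference outcome.** Assume a gonorrhoea rate of 0.0046 over 2.6 to 4.0 years (0.0046/4.0 = 0.00115 to 0.0046/2.6 = 0.00177 per year), chlamydia 3 to 5 times as frequent, exposed zero time 1 year later, and r = 5. Approximating the exposed hazard factor by 1/(1 + (r − 1) × rate × lag), a true HR of 1.00 for chlamydia becomes:
- 1/(1 + 4 × 3 × 0.00115) = 0.986
- 1/(1 + 4 × 5 × 0.00177) = 0.966

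Both are below the 1.0 threshold through the counting rule alone.

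**4. Carry-over under the SAP rule.** Express carry-over cases as multiples cE and cC of the genuine reference risk. Then HR observed ≈ (HR + cE)/(1 + cC). If cE = cC = c, VE observed = VE/(1 + c), so a real effect is diluted and a null stays null. If they differ, the sign is open: at HR 0.80, VE rises whenever cE is below 0.80 × cC. The documents give nothing from which to set c.

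**The case against.** The strongest reply is that the protocol never states a cancelling rule. The sentence on first episodes closes a section that has just started follow-up 14 days after zero time and ended it at the outcome. Read with 9.7, it most naturally means that follow-up stops at the first event. The SAP, which may modify the protocol, limits the primary outcome to follow-up in 2.1, 5.1.1 and 7.2.1.1. Its analysis sections for chlamydia also restate the 14-day start. All of this stands, so cancellation is only one literal reading.

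A reader might go further and infer that the rule removes events mainly from exposed people and so inflates VE. The documents do not support that. Trumenba after MenACWY is an ordering within a person; it does not show that exposed people have more look-back than reference people. The protocol indexes the reference cohort at its last MenACWY dose, which narrows any gap. The gap is clearest under the SAP's first-dose index, but the SAP lacks the unanchored wording. In number, most cancelled events would fall in the reference cohort, which is about 85% of the sample.

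The reply does not answer the missing washout. Anchoring to follow-up leaves a repeat claim after day 14 counting as a new case.

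**Conclusion.** The concern holds as an inconsistency and an omission. The protocol's first-episode wording is not tied to zero time, the SAP's case definitions are not uniform, and nothing separates a new episode from continued coding of an old one.

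The size is probably small. With twice the prior infections in the exposed cohort, the literal reading moves a null result by 0.6 points or less for r up to 5 and an exposed share up to 0.24%, and by about 4.4 points for r = 20 and 0.48%. It vanishes with equal shares and reverses if the reference cohort has more. Its direction therefore depends on which reference index date is used. A VE of 25.0% from a true 20% can be produced with the lag formula, 1 − 0.80/(1 + 19 × 0.00177 × 2), but only with repeat risk, lag and event rate all at the top of their assumed ranges. It should not be taken as the expected bias.

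The effect of carry-over cannot be sized from the documents. The practical consequence is greatest for chlamydia, because a shift of a few hundredths in its hazard ratio could be read as confounding. All sizes rest on assumed values of q, r, lag and relative frequency.

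**What to change.** 1. In both documents and for both outcomes, define the event as the first new episode starting at least 14 days after zero time. Replace the protocol's study-period wording and the SAP's database wording with this.
2. Add a carry-over rule: a code within a fixed window of an earlier code for the same infection belongs to the same episode. Thirty days is one option, but the sponsor must justify it, because the 30-day window in SAP 7.2.1.2 defines gonorrhoea–chlamydia coinfection, not repeat episodes. Run a longer window as a sensitivity analysis.
3. Adjust for prior infection, measured over a fixed look-back of equal length in both cohorts.
4. Reconcile the reference index date between Protocol 9.1 and SAP 2.1.
5. Before fitting the outcome models, report by cohort the number of people with a prior code and the observed time before zero time. This replaces the assumed q with data.

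The cost is a few sentences in each document and an episode rule in the code, using claims already in hand. A few carry-over cases are lost. People with short enrolment before zero time, including those indexed early in 2016, will have incomplete look-back. Neither document requires pre-index enrolment, so the SAP must say how they are treated.
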